## **12. HANDLING OF MISSING OR INCOMPLETE DATES FOR ADVERSE EVENTS AND CONCOMITANT MEDICATIONS**

### **12.1 Imputation Rules for Partial or Missing Stop Dates**

If the month and year are present, impute the last day of the month. If only the year is present, impute December 31 of that year. If the stop date is entirely missing, assume the event or medication is ongoing. If a partial or complete stop date is present and the 'ongoing' or 'continuing' box is checked, then it will be assumed that the AE or concomitant medication stopped and the stop date will be imputed, if partial.

		Stop Date						
		Complete: yyyymmdd		Partial: yyyymm		Partial: yyyy		Missing
Start Date		<1 st Dose	≥1 st Dose	<1 st Dose yyyymm	≥1 st Dose yyyymm	<1 st Dose yyyy	≥1 st Dose yyyy	
Partial: yyyymm	=1 st Dose yyyymm	2	1	2	1	N/A	1	1
	≠ 1 st Dose yyyymm		2		2	2	2	2
Partial: yyyy	=1 st Dose yyyy	3	1	3	1	N/A	1	1
	≠ 1 st Dose yyyy		3		3	3	3	3
Missing		4	1	4	1	4	1	1

1 = Impute the date of first dose

2 = Impute the first of the month

3 = Impute January 1 of the year

4 = Impute January 1 of the stop year

Note: For patients who were never treated (first dose date is missing), partial start dates will be set to the first day of the partial month.

Note: If the start date imputation leads to a start date that is after the stop date, then do not impute the start date.

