5.1 Description of Study Visits

5.1.1 Visit -1 (Day -28 through Day 0, in-clinic): Screening

The following procedures will be performed:

- Obtain written informed consent before the start of any study specific procedure.
- Review medical history including all previous treatments for OA
- Record prior and concomitant medications including start/stop dates, indication, dose and frequency
- Record demographic data including year of birth, age, gender and race
- Measure and record height and weight
- Perform and record physical examination
- Record KL Grade from radiological assessment that is not older than 6 months prior to screening. Patient may have an x-ray at screening in order to satisfy this requirement
- Record pain in the index knee with the WOMAC Index 3.1 using both the 5-point Likert scale and the 100mm VAS scale
- Record pain in the contralateral knee with the WOMAC Index 3.1 pain subsection using both the 5-point Likert scale and the 100mm VAS scale
- Record vital signs. (Measure body temperature, systolic blood pressure [SBP], diastolic blood pressure [DBP] and pulse rate)
- Evaluate all inclusion and exclusion criteria to ensure that patients meet all inclusion criteria and none of the exclusion criteria
- Review collection instructions of daily diary pain scores with subject

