## **Treatment failure**

Treatment failures are defined as patients who receive additional medications or surgical procedures in order to treat worsened symptoms in the treated knee during the study; specifically, treatment failures are any patients who:

- Increase their corticosteroid dose of  $\leq 10$  mg above their starting dose of corticosteroid during the study to treat worsened symptoms in the treated knee;
- Increase use of NSAID pain medications by a clinically significant amount during the study to treat worsened symptoms in the treated knee;
- Begin opioid treatment during the study to treat worsened symptoms in the treated knee;
- Receive intra-articular injection of pain medicine in the treated knee during the study to treat worsened symptoms in the treated knee;
- Undergo total knee replacement or other surgical procedure in the treated knee prior to assessment of the primary efficacy endpoint.

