## **7.2 Handling of Missing and Incomplete Data**

All data collected under this study protocol will be included in the assessment of patient safety. Missing or incomplete AE data will assume greatest relationship to study drug and/or severity. Incomplete adverse event and concomitant medication dates will be imputed as described in Section 12. If imputed dates are used, then they will be identified as such in the final study report. If an AE start date is missing or partially missing and no additional information is available from the site in order to establish whether the event started before or after the dose of study drug, the event will be considered to have started after dose. Partially missing dates where the month and year is prior to Day 0 will be classified as pre-dose.

For the co-primary effectiveness analysis of WOMAC pain change and WOMAC C function change, missing change scores will be imputed when the ITT analysis population is used. Missing data will be imputed by the fully conditional specification predictive mean matching multiple imputation approach of Berglund and Heeringa (2014). A sensitivity analysis will be conducted in which the missing 12-week endpoint is replaced by the Baseline WOMAC pain score.

For the secondary endpoints of PGA, 100mm VAS, and number of acetaminophen pills used, missing values will be imputed when the ITT analysis population is used. Imputation methods employed will be multiple imputation (SAS PROC MI and SAS PROC MIANALYZE) and single imputation methods (i.e., regression-based estimates, Baseline imputation, LOCF, and a worst/best case imputation).

Per the WOMAC User Guide, the patient's response will be regarded as invalid, and the subscale(s) deficient, in the event that two pain, both stiffness, or more than four physical function items are omitted. Further, if one pain, one stiffness, or 1-3 physical function units

are missing, the average value for the subscale will be substituted in lieu of the missing item value(s).

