### **14.3 Safety**

14.3.1	Overall Summary of Treatment-Emergent Adverse Events (Analysis population: Safety)
14.3.2	Incidence of Treatment-Emergent Adverse Events by System Organ Class and Preferred Term (Analysis population: Safety)
14.3.3	Incidence of Treatment-Emergent Adverse Events by System Organ Class and Preferred Term by Maximum Severity (Analysis population: Safety)
14.3.4	Incidence of Treatment-Emergent Related Adverse Events by System Organ Class and Preferred Term (Analysis population: Safety)
14.3.5	Incidence of Treatment-Emergent Related Adverse Events by System Organ Class and Preferred Term by Maximum Severity (Analysis population: Safety)
14.3.6	Incidence of Treatment-Emergent Serious Adverse Events by System Organ Class and Preferred Term (Analysis population: Safety)
14.3.7	Incidence of Treatment-Emergent Adverse Events by Preferred Term in Descending Order of Frequency (Analysis population: Safety)
14.3.8	Incidence of Treatment-Emergent Related Adverse Events by Preferred Term in Descending Order of Frequency (Analysis population: Safety)
14.3.9.1	Summary of Vital Signs and Change from Baseline over Time for Pulse (bpm) (Analysis population: Safety)
14.3.9.2	Summary of Vital Signs and Change from Baseline over Time for Temperature (F) (Analysis population: Safety)
14.3.9.3	Summary of Vital Signs and Change from Baseline over Time for Systolic BP (mmHg) (Analysis population: Safety)

14.3.9.4	Summary of Vital Signs and Change from Baseline over Time for Diastolic BP (mmHg) (Analysis population: Safety)
14.3.9.5	Concomitant Medication Use by ATC Level 1 and WHO Preferred Term (Analysis population: Safety)
14.3.9.6	Medication Started on Study by ATC Level 1 and WHO Preferred Term (Analysis population: Safety)
14.3.9.7	Concomitant Medications by WHO Preferred Term in Descending Order of Use (Analysis population: Safety)
14.3.9.8	Medication Started on Study by WHO Preferred Term in Descending Order of Use (Analysis population: Safety)

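### SAP 12.1 can date a medication already recorded at Screening to the day of injection, so it may be tabulated as started on study

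*SAP*

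**What the plan says.** SAP 7.2 sends incomplete adverse event dates and incomplete concomitant medication dates to the same rules in SAP Section 12.

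For stop dates, SAP 12.1 has three rules. A stop that lacks only the day goes to month end. For a year-only stop the rule is "If only the year is present, impute December 31 of that year". Where no stop was recorded at all, it is "If the stop date is entirely missing, assume the event or medication is ongoing".

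For start dates, SAP 12.1 gives a grid of recorded start against recorded stop. The entry that matters here is "1 = Impute the date of first dose". Codes 2, 3 and 4 assign the first of the recorded month, 1 January of the recorded year, and 1 January of the stop year. A note leaves the start unimputed if it would fall after the stop.

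SAP 7.2 adds two safeguards. A partial date whose month and year precede Day 0 is treated as pre-dose. For adverse event start dates only, the event is assumed to follow dosing when "no additional information is available from the site in order to establish whether the event started before or after the dose of study drug".

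Protocol 5.1.1 requires sites at Screening to "Record prior and concomitant medications including start/stop dates, indication, dose and frequency". SAP 10.1 plans Table 14.3.9.6, "Medication Started on Study by ATC Level 1 and WHO Preferred Term", and Table 14.3.9.8, which gives the same medications in descending order of use. The SAP does not define when a medication counts as started on study.

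**The concern.** For an adverse event of unknown onset, assigning the date of first dose is the cautious choice, because it keeps the event in the treatment-emergent tables. The same rule is not cautious for a medication. A drug written down at Screening is known to have been started before the injection, so a Day 0 start contradicts the trial's own record. SAP 7.2 allows outside information to settle the order of events for adverse event starts but offers nothing equivalent for medications.

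At stake is the meaning of the two started-on-study tables, which a reader would use to see whether one arm needed more added medication. Long-standing treatment dated to Day 0 would be mixed with treatment that really was new. The year-end stop rule raises a smaller, separate problem: it can make a finished course appear to have been in use during the study.

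**Working it through.** The plan gives no figure to reproduce, and no power or alpha calculation applies. The check was to apply the SAP 12.1 rules to incomplete dates for medication truly begun before dosing.

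**The grid.** It has 5 start rows and 7 stop columns, so 5 × 7 = 35 cells, counting merged cells singly. Code 1 fills 12 cells and 2 are not applicable. The other 35 − 12 − 2 = 21 keep the recorded month or year, or use the stop year. Code 1 applies when the start is missing, in the dosing month, or year-only in the dosing year, and the stop is missing or not known to be before first dose.

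**Test patterns.** Seventeen start/stop combinations were run with an assumed first dose on 15 September 2019. The eleven that start on Day 0 or remain concomitant are:

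| Recorded start | Recorded stop | Code | Imputed start | Imputed stop |
|---|---|---|---|---|
| missing | missing | 1 | 15 Sep 2019 | ongoing |
| 2019 | missing | 1 | 15 Sep 2019 | ongoing |
| Sep 2019 | missing | 1 | 15 Sep 2019 | ongoing |
| 2019 | 2019 | 1 | 15 Sep 2019 | 31 Dec 2019 |
| missing | 2019 | 1 | 15 Sep 2019 | 31 Dec 2019 |
| missing | Sep 2019 | 1 | 15 Sep 2019 | 30 Sep 2019 |
| Sep 2019 | Sep 2019 | 1 | 15 Sep 2019 | 30 Sep 2019 |
| 2015 | missing | 3 | 1 Jan 2015 | ongoing |
| Jun 2019 | missing | 2 | 1 Jun 2019 | ongoing |
| 2018 | 2019 | 3 | 1 Jan 2018 | 31 Dec 2019 |
| Mar 2019 | 2019 | 2 | 1 Mar 2019 | 31 Dec 2019 |

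The other six all have a stop known to precede dosing (for example, missing start with stop August 2019). They stay wholly pre-study.

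**Results.**

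- Moved to a Day 0 start: 7 of 17. The start grid does the moving in all 7. The 31 December rule is involved in 2 of them, and there it also prevents the start-after-stop note from triggering.
- Not moved: 17 − 7 = 10. Of these, 4 count as concomitant. Two of the 4 are correctly ongoing. The other two (2018 to 2019, and March 2019 to 2019) overlap the study only because the stop is set to 31 December.
- With first dose assumed on 10 January 2020 and the same recorded dates, only missing/missing is moved: 1 of 17. The 2019 dates then belong to an earlier year, and codes 2 to 4 handle them.

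So the ongoing medication with no known start is re-dated whatever the calendar date of dosing. The other six moved patterns depend on the recorded date falling in the dosing month or year. These are counts of date patterns, not estimates of how many records are affected.

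**The case against.** The strongest reply is that the rules mostly work. Codes 2 and 3 keep a known earlier month or year pre-dose, code 4 does so for a missing start with a pre-dose stop, and the pre-dose sentence in SAP 7.2 is not limited to adverse events. All of that stands: it would be wrong to say that the rules move pre-study medication into the study in general.

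It can also be said that Section 12 covers concomitant medication only, since the schedule lists prior medications separately. This weakens the year-end stop case for a course known to have ended before consent. It does not settle the matter, because SAP 8.5.1 tabulates medications taken before as well as during the study under the same heading. It does not touch the ongoing drug with an unknown start, which is concomitant on any reading.

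Sites must record start and stop dates, and Protocol 11.7.1 provides for discrepancy queries. That should reduce the number of incomplete dates but does not change what the rule does with those that remain.

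Four stronger readings are tempting, and the documents do not support them:

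- **False treatment failures.** A reader might infer that a Day 0 opioid start becomes a failure. The SAP 5.2 item is "Begin opioid treatment during the study to treat worsened symptoms in the treated knee", so it needs a reason as well as a date, and the NSAID and corticosteroid items need an increase. Neither document says that failures are derived from imputed dates.
- **Changes to the per-protocol set.** These too would require deviations or failures to be programmed from imputed dates, which is not stated.
- **Breaches of exclusion criterion 11.** That window is the four weeks before randomization. Code 1 gives Day 0, which SAP 5.2 also makes the randomization day.
- **A large count of affected records.** One could assume 3 to 5 medications per patient with 5% to 20% incompletely dated, giving 1,034 × 3 × 0.05 ≈ 155 to 1,034 × 5 × 0.20 = 1,034 records. Neither input is in the documents, and the product ignores records protected by a pre-dose stop.

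**Conclusion.** The point holds in a narrow form. A stated rule gives a wrong date for a recognisable kind of record: a medication known before injection whose start is missing, in the dosing month, or year-only in the dosing year, with no stop known to precede dosing. Listing it in Tables 14.3.9.6 and 14.3.9.8 follows only if Day 0 counts as on study. The year-end stop rule is a second, lesser defect, which rests on Section 12 being applied to courses that had already ended.

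The size is unknown, because the documents give no rate of incomplete dates. The established reach is the medication tables. Any effect on the exploratory Fisher's exact test of treatment failures or on the per-protocol re-analysis depends on a programming choice that the documents neither state nor rule out. This is a modest correction to make before the SAP is final, which Protocol 10.3.10 places before unblinding at the interim analysis.

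**What to change.** Add a medication-specific rule to SAP 12.1:

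- For any medication recorded at Screening, or at Visit 1 before injection, do not impute a start on or after Day 0; classify it as prior or ongoing.
- If that record shows the medication as already stopped, cap the imputed stop at the date of that visit.
- Keep code 1 for medications first reported after injection.

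Then define started on study for Tables 14.3.9.6 and 14.3.9.8, including whether Day 0 counts. State in the treatment-failure definition that failures are determined from recorded starts, dose changes and reasons, not from imputed dates.

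The cost is a few lines of SAP text and some programming, with no new assessment. The programming needs the visit or entry date of each medication record. The documents do not say that the database keeps it, so the sponsor should confirm this first.

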## 13. SCHEDULE OF ASSESSMENTS AND PROCEDURES

	Screening	Pre-Baseline (phone)	Baseline	24-hours (phone)	Week 2 (phone)	Week 4 (phone)	Week 6	Week 8 (phone)	Week 10 (phone)	Pre-Week 12 (phone)	Week 12	Week 24	Early Term.
Assessments & Procedures	Visit -1 Day-28 to 0	Visit 0 Day -6 to 0	Visit 1 Day 0	Visit 2 Day 1	Visit 3 Day 14 ± 7	Visit 4 Day 28 ± 7	Visit 5 Day 42 ± 7	Visit 6 Day 56 ± 7	Visit 7 Day 70 ± 7	Visit 8 Day 77 ± 7	Visit 9 Day 84 ± 7	Visit 10 Day 174 ± 7	
Informed Consent	X												
Inclusion/exclusion criteria	X		X										
Medical history/prior medications	X		X										
Concomitant medications	X		X	X	X	X	X	X		X	X	X	
Urine sample			X**								X		
Physical examination	X		X				X				X	X	X
Vital Signs	X		X				X				X	X	X
Randomization			X										
Review Diary Completion Instructions	X								X				
Phone Contact Daily Collection Reminder		X									X		
WOMAC A (Likert)	X	X*	X***		X	X	X	X	X	X*	X***	X	X
WOMAC A (VAS)	X	X*	X***							X*	X***		X
WOMAC B and C (Likert)	X		X		X	X	X	X			X	X	X
PGA	X		X		X	X	X	X			X	X	X
X-ray 	X												
Study treatment			X										
Dispense Rescue medication			X										
Review Rescue medication				X	X	X	X	X	X		X	X	X
Adverse Events			X	X	X	X	X	X	X		X	X	X

Visits are in clinic except for Day 1 and Weeks 2, 4, 8 and 10 when patients will be contacted by telephone

X-ray may be acquired at Screening to satisfy inclusion criteria, "Index knee must be symptomatic for greater than six months with a clinical diagnosis of OA and supported by radiological evidence (KL 4) that is not older than six months prior to the date of screening".

\*Patients will complete 7 daily pain score assessments up to and including the Baseline and Week 12 visits to allow calculation of WOMAC A weekly pain scores. The Screening and first Pre-Baseline daily pain score collection may occur on the same day, in office or at home, as appropriate.

\*\*Urine will only be collected at Baseline if necessary to conduct a pregnancy test; collection to occur as applicable

\*\*\*The WOMAC may occur in office or at home, and may serve as the 7th WOMAC Daily Pain collection
